2.1.6 Hypotheses

Aim 1: To determine the prevalence of ATTR CA in Caribbean Hispanics and Blacks with HF

Hypothesis 1. Overall prevalence of ATTR CA: The prevalence of ATTR CA will be defined by the number of cases with both ATTRwt and ATTRm CA as a percentage of total enrollment. The background prevalence of Val122Ile in the US Black population is 3.4%, and we hypothesize a prevalence rate of 8% of ATTRm Val122Ile in our outpatient HF population. Since there are no data in Hispanics regarding ATTR CA prevalence, we further hypothesize that we will observe a prevalence of ATTRwt CA of 2-8% of the Hispanic population. Thus, we have conservatively defined the predicted prevalence of ATTR CA as 10-15%.

Hypothesis 2. Relative proportion of ATTR CA comprised by ATTRwt and ATTRm: As noted above, based upon the background allele frequency, we anticipate that Black patients will be much more likely to manifest ATTRm (Val122Ile) vs. ATTRwt CA, whereas Hispanic patients will be more likely to manifest ATTRwt CA. We will be able to explore the Val122Ile genotype frequency in the Hispanic population, and with the addition of cardiac amyloid scintigraphy scanning, the relative contribution of ATTRm in this population, which we postulate to be lower than Blacks. We will utilize genetic ancestry analysis data to further characterize race and ethnicity, and, as an exploratory analysis, evaluate the interaction of genetic variants identified with Val122Ile and ATTR CA as defined by radiotracer uptake.

Hypothesis 3. Proportion of gender: Published reports of ATTR Val122Ile are 75% male and reports of ATTRwt are 95% male. We hypothesize that highly sensitive cardiac amyloid scintigraphy testing will reveal a gender distribution of ATTR that is closer to 50%, based upon allele distribution. We will explore comorbidities, TTR stability, and RBP4 differences among men and women with ATTR to determine interactions with phenotypic expression.

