2.1.7 Statistical Considerations and Sample Size

Power and Sample Size: The total enrollment proposed for this study is of 800 subjects: 600 Blacks and 200 Hispanics. Amongst them, we expect approximately 80-160 ATTR CA subjects and 640-720 non-amyloid controls. The sample size planned for each race/ethnicity group achieves 80% power to

detect, as in Aim 1: (1) a prevalence of ATTR-CA of 10-15%, (2) a two-fold difference in the prevalence of ATTRm between Blacks and Hispanics (i.e., 0.08 vs 0.04, respectively), as well as, a similar difference in the prevalence of ATTRwt between Blacks and Hispanics, (3) a difference as small as 0.03 (if one truly exists) in the prevalence of ATTRwt with respect to gender (male) distribution between the two race/ethnic groups, and (4) in the ATTR CA group alone, we plan to measure the hierarchical composite endpoint of death, heart failure hospitalization, and 30% decline in 6-minute hall walk after 1 year. A two-sided logrank test with an overall sample size of 80 subjects (40 in the ATTRwt and 40 in the ATTRm) achieves 82% power at a 0.05 significance level to detect a hazard ratio (HR) of 0.44 when the proportion of patients that did not progress in the mutant group is 0.60. This corresponds to a minimum difference of 15% in the probability of not having progressed past 12 months between the two groups.

Aim 2 focuses on comparing differences in TTR kinetic stability and RBP4 concentration between ATTR CA (N=80-120) and the non-amyloid group (N=680-720). These sample sizes generate >95% power to detect: Hypothesis 1) a minimum difference in RBP4 of 5, assuming SDs of 9 and 20 for ATTR CA and non-amyloid, respectively; Hypothesis 2) a mean change difference in TTR stability as small as 0.01, SD of 0.002.

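### Section 2.1.7 states 82% power for Hypothesis 4, but the design as written has about 50%, and the genotype split its own prevalences imply has about 38% at 80 cases and about 67% at 120

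*Combined protocol and SAP*

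**What the plan says.** All of the sizing is in section 2.1.7, Aim 1 item (4). The endpoint is the "hierarchical composite endpoint of death, heart failure hospitalization, and 30% decline in 6-minute hall walk after 1 year". The comparison is "A two-sided logrank test with an overall sample size of 80 subjects (40 in the ATTRwt and 40 in the ATTRm"), and the claim is that this "achieves 82% power at a 0.05 significance level to detect a hazard ratio (HR) of 0.44". The event rate behind that claim is fixed by a further condition, that it applies "when the proportion of patients that did not progress in the mutant group is 0.60". The text then adds: "This corresponds to a minimum difference of 15% in the probability of not having progressed past 12 months between the two groups".

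The same section gives what is needed to work out the genotype split. On enrolment: "The total enrollment proposed for this study is of 800 subjects: 600 Blacks and 200 Hispanics". Item (2) uses "a two-fold difference in the prevalence of ATTRm between Blacks and Hispanics (i.e., 0.08 vs 0.04, respectively"). Section 2.1.7 expects 80-160 ATTR-CA cases under Aim 1 and 80-120 under Aim 2. Section 2.1.6, Hypothesis 1, predicts an overall prevalence of 10-15%.

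Section 2.1.6, Hypothesis 2, also predicts an imbalance in the larger enrolment group: "Black patients will be much more likely to manifest ATTRm (Val122Ile) vs. ATTRwt CA".

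**The concern.** Genotype is observed, not assigned, so the ATTRm and ATTRwt group sizes follow from who is enrolled and from the prevalences. The plan assumes 40 and 40 without deriving it, and its own prevalences give a different split at the 80 cases used for sizing. ATTRwt is then the smaller group and also has the lower assumed hazard, so it supplies very few events.

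Separately, about 24 events are expected from 80 patients in one year on the stated inputs. That is too few for 82% power at a hazard ratio of 0.44.

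Genotype-phenotype association is part of the primary objective (section 2.1), and Hypothesis 4 is its progression test. Read against a stated 82%, a null result would look like evidence that genotype does not matter. At 38% it would say little.

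**Working it through.** **Inputs (section 2.1.7 unless noted).** Two-sided alpha 0.05; HR 0.44 (ATTRwt relative to ATTRm); ATTRm event-free proportion 0.60 at 12 months; 600 Black and 200 Hispanic subjects; ATTRm prevalence 0.08 and 0.04; overall prevalence 10-15% (section 2.1.6). The 0.08 and 0.04 are read as cardiac amyloidosis, not carrier status, because section 2.1.6 combines the 8% with an ATTRwt rate to reach 10-15%.

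**1. The plan's own figure, at 40 v 40.**
- ATTRwt event-free: 0.60^0.44 = 0.799.
- Expected events: 40 x 0.40 + 40 x 0.201 = 16.0 + 8.05 = 24.05.
- Schoenfeld: 0.821 x sqrt(24.05 x 0.25) - 1.96 = 0.05, power 52%.
- Freedman: sqrt(24.05) x 0.56/1.44 - 1.96 = -0.05, power 48%.
- Simulated logrank (exponential times, all censored at 12 months): 50%.

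Reaching 82% needs about 50 events by Schoenfeld or 55 by Freedman, roughly twice what is expected. Other readings at 40 v 40, by Schoenfeld, also fall short: one-sided 64%; 0.60 taken as the proportion that progressed 71%; 0.60 taken as the ATTRwt proportion 77%. Eighty per group (48.1 events) gives 81%, but the text says 80 overall.

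**2. The split the plan implies.**
- ATTRm: 0.08 x 600 + 0.04 x 200 = 48 + 8 = 56.
- Total cases: 10% of 800 = 80; 15% of 800 = 120.
- ATTRwt: 80 - 56 = 24, up to 120 - 56 = 64. At 160 cases, 160 - 56 = 104.

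**3. Power at that split** (simulated two-sided logrank, as in step 1). Expected events are 0.40 x ATTRm + 0.201 x ATTRwt. The last column uses the HR that matches a 15-point difference (step 5).

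| ATTRm v ATTRwt | Cases | Expected events | Power, HR 0.44 | Power, HR 0.563 |
|---|---|---|---|---|
| 40 v 40 (as written) | 80 | 16.0 + 8.05 = 24.05 | 50% | 30% |
| 56 v 24 | 80 | 22.4 + 4.83 = 27.2 | 38% | 22% |
| 56 v 64 | 120 | 22.4 + 12.9 = 35.3 | 67% | 43% |
| 56 v 104 | 160 | 22.4 + 20.9 = 43.3 | 78% | 52% |

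**4. Dependence on method.** At 56 v 24, Freedman gives 36%, a two-proportion calculation 40% and Schoenfeld 50%. Schoenfeld is optimistic here. It assumes events divide as patients do, so its information term is 27.2 x 0.7 x 0.3 = 5.7. The expected events divide 22.4 to 4.83, and 1/(1/22.4 + 1/4.83) = 4.0, which gives 37%. Simulating the planned test is the better reference.

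**5. The stated difference.** HR 0.44 with 0.60 gives 0.799 - 0.60 = 0.199, a 20-point difference, not 15. A 15-point difference is 0.60 v 0.75, so HR = ln 0.75 / ln 0.60 = 0.563.

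None of these figures allows for loss to follow-up. Section 2.2 censors subjects who enter investigational trials, which can only lower them.

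**The case against.** The strongest reply is that 80 is the bottom of the expected range and 40/40 is an idealised floor. This partly stands. At 12% prevalence there are 96 cases, 56 v 40, and power is 54-55%. At the 12.5% midpoint there are 100 cases, 56 v 44, and it is about 58%. Both exceed the 50% at 40 v 40, so the split lowers power below the equal-split figure only near the bottom of the range. But item (4) states its power at 80 cases, and there the implied split is 56 v 24.

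It can also be said that the split costs only about 2 points by Schoenfeld (52% to 50%). That is so, but the formula is unreliable when the larger group also has the higher hazard (step 4 of the working).

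It is also true that a hazard ratio with a 95% confidence interval is already planned for Hypothesis 4 in section 2.1.8, so nothing needs adding there.

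A reader might infer more than the documents support:
- **That case mix explains the whole fall from 82%.** It does not. About 32 of the 44 points (82% to 50%) are present at 40 v 40.
- **That 40 ATTRwt cases is the most the plan can yield, or that power could be as low as 14%.** Both rest on a Black ATTRwt rate of 1-4%, which the plan never states. It is an assumption made by halving the Hispanic 2-8%, and it gives 10-40 ATTRwt. The plan's overall prevalence gives 24-64. The 14% case (56 v 10) has 66 cases, below the plan's minimum of 80. It is a sensitivity case at most.
- **That the 82% came from reading 80 per group as 80 in total.** The figure is close (81%), but nothing in the documents shows how it was obtained.

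**Conclusion.** The concern holds in this form. The 82% does not reproduce on the stated inputs: 40 v 40 gives about 50%. The 40/40 split conflicts with the section's own ATTRm prevalences, and at 80 cases the implied 56 v 24 takes power down about another 12 points, to about 38%. Across 80-120 cases power is about 38% to 67%, and it remains below 82% at 160 cases.

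This assumes exponential event times, a 12-month cut with no dropout, HR 0.44, and 56 ATTRm cases. If section 2.1.6's 8% is applied to all 800 subjects instead, there are 64 ATTRm cases; power is then about 26% at 80 cases (64 v 16) and 66% at 120 (64 v 56), so the conclusion does not depend on that choice. If the intended effect is the 15-point difference, every figure is lower: about 22% at 56 v 24 and 43% at 56 v 64.

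The error is in a stated power, not in the design or the analysis method, and rewording corrects it.

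**What to change.** In section 2.1.7, Aim 1 item (4):
- Replace the 40/40 sizing with the implied split: 56 ATTRm v 24 ATTRwt at 80 cases, and 56 v 64 at 120.
- Restate power for HR 0.44 as about 38% to 67% over that range, naming the method (simulated two-sided logrank, exponential times, 12-month cut, no dropout).
- Reconcile the hazard ratio with the absolute difference. Either keep 0.44 and print a 20-point difference, or keep 15 points, print an HR of about 0.56, and give power as about 22% to 43%.
- If a lower ATTRwt yield is shown, label it a sensitivity case and state the assumed Black ATTRwt rate.

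The cost is a less favourable stated power for Hypothesis 4. No patients, procedures or analyses are added.

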Hypothesis 4. Progression of disease: Markers of disease progression are lacking in ATTR CA. We hypothesize that attainment of a hierarchical composite endpoint at 1-year of death, heart failure hospitalization, and 30% decline in 6-minute hall walk will be higher in ATTRm vs. ATTRwt CA. In addition, we will explore the capacity of specific markers to assess disease progression including: (1) established circulating biomarkers such as troponin I/T, NT-proBNP, BNP and Galectin-3, (2) novel biomarkers such as RBP4 and TTR concentration, (3) ECG, and

echocardiographic measures including longitudinal strain and MCF, (4) functional capacity by 6-minute hall walk and SPPB, and (5) QOL. Our preliminary data and published work⁹ suggests reduced median survival for ATTRm Val122Ile CA (25 months) vs ATTRwt (43 months) in different race cohorts. We hypothesize that we will observe reduced survival and greater functional decline in ATTR Val122Ile vs ATTRwt within race cohorts.

Hypothesis 5. Performance of risk calculator: Our point-of-care risk calculation utilizing RBP4 and TTR concentration with echocardiographic and ECG determined parameters will be tested in this cohort. We will re-derive the prediction model based upon clinical variables noted above. We anticipate showing a similar degree of accuracy (ROC AUC > 0.95) for identification of cases with ATTR vs. controls

Specific Aim 2: To demonstrate that circulating RBP4 concentration is integral to TTR tetramer stability, which in turn determines the clinical characteristics of ATTR CA. We will measure TTR tetramer stability and RBP4 concentration in serum and urine collected in Aim 1. The overall hypotheses of this Aim are that measurements of TTR kinetic stability, RBP4 and TTR concentration will differentiate patients with ATTR CA vs. non-amyloid HF controls and associate with disease progression and outcomes. Specific hypotheses are as follows:

Hypothesis 1: TTR kinetic stability and RBP4 concentration: We hypothesize that at baseline, TTR kinetic stability will be lower in ATTR CA vs. non-amyloid HFpEF, and that stability will be inversely proportional to plasma RBP4 concentration. We further hypothesize that TTR kinetic stability will be lower for ATTRm vs. ATTRwt.

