2.1.8 Data Analysis Plan

Descriptive statistics will be used to summarize subjects' demographics and study outcomes. Sample proportions with exact 95% confidence intervals will be used to estimate the overall prevalence of ATTRm CA in Blacks and Hispanics and by sex. All analyses will be performed in SAS v.9.4 (Cary,NC), at a significance level of 0.05.

AIM 1: Hypotheses 1-3: The differences in proportions for prevalence (#1), genetic mutation status (#2), and sex (#3) will be assessed using Chi-squared/Fisher Exact tests. The genetic ancestry analysis will use 500K SNP data to perform principal components analysis (PCA) and determine the percentage of African admixture in all participants. To identify the associations of rare genetic variants in the TTR gene in ATTR CA cases vs controls, we will utilize burden testing.⁹⁴ **Hypothesis 4:** The main analysis will use the Kaplan-Meier method to estimate the probabilities of the composite endpoint, with medians (95% CI) being reported for each group. Cox regression analysis will be performed to generate the hazard ratio (95% CI), and to allow adjustment for other covariates such as sex or race/ethnicity, or explore interaction with other variables including cardiac biomarkers, echo parameters, or QOL. Alternatively, we will apply and compare Finkelstein-Schoenfeld's unmatched approach⁹⁵ to the matched win ratio,⁹⁶ both methods being used for reporting composite endpoints, with more appropriate priority given to the more clinically important event, e.g. mortality. **Hypothesis 5:** We will test the clinic-based risk calculator that was previously developed and validated in a smaller matched cohort study.⁹⁷ The proposed 4-variable model included: RBP4, LVEF, inter-ventricular septal thickness, mean limb lead QRS voltage, and generated an ROC AUC >90%. This model will be tested in our larger cohort and assessed with respect to prediction capability (AUC ROC) and goodness-of fit (Hosmer-Lemeshow test). We also plan to fit additional multivariable logistic regressions using the variables collected employing variable selection/model-building strategies and comparing the

resulting model(s) to the one proposed above. The variables in the final clinical risk model will be based on weights from the multivariate model.

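### Section 2.1.7: 40 ATTRwt plus 40 ATTRm gives about 50% logrank power for HR 0.44, not 82%, and that HR means a 20-point difference at 12 months, not 15

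*Combined protocol and SAP*

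**What the plan says.** Section 2.1.6, Aim 1, Hypothesis 4 sets out the comparison: "We hypothesize that attainment of a hierarchical composite endpoint at 1-year of death, heart failure hospitalization" and a 30% fall in six-minute walk distance, expected to be more frequent in ATTRm than in ATTRwt.

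Section 2.1.7 gives the power for it. The design is "A two-sided logrank test with an overall sample size of 80 subjects (40 in the ATTRwt and 40 in the ATTRm" groups), which "achieves 82% power at a 0.05 significance level to detect a hazard ratio (HR) of 0.44", with 0.60 of the mutant group not progressed. The next sentence translates this into a "minimum difference of 15% in the probability of not having progressed past 12 months between the two groups". Earlier in the same section the plan says of the 800 enrolled that "we expect approximately 80-160 ATTR CA subjects and 640-720 non-amyloid controls".

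For the analysis, section 2.1.8 plans the Kaplan-Meier method "to estimate the probabilities of the composite endpoint, with medians (95% CI) being reported for each group", together with a Cox hazard ratio and its 95% CI.

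**The concern.** The 0.60 and the hazard ratio together fix the ATTRwt proportion, the expected number of events and hence the power. They also fix the absolute difference. Neither printed result matches.

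Section 2.1.1 lists progression among the hypotheses to be tested under Specific Aim 1, and this is its only power statement. A reader would conclude that 80 cases are enough to detect a 15-point difference with 82% power. If that is wrong, a non-significant result could be misread as evidence against a genotype effect.

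**Working it through.** **Inputs, all from section 2.1.7 unless noted.** Two-sided logrank test, significance level 0.05; 40 ATTRm and 40 ATTRwt; proportion not progressed in ATTRm 0.60; HR 0.44. The direction (ATTRm worse, so the HR is ATTRwt relative to ATTRm) comes from Hypothesis 4 in 2.1.6. The horizon is 12 months: the endpoint is assessed after 1 year and the synopsis gives participation of about 12 months. The power statement has no dropout allowance, so none is used here.

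**Step 1, effect size.** Under proportional hazards S_wt = S_m^HR = 0.60^0.44 = 0.799. The difference is 0.799 − 0.600 = 0.199, or 20 points. For 15 points, HR = ln 0.75 / ln 0.60 = 0.563.

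**Step 2, events.** 40 × (1 − 0.600) + 40 × (1 − 0.799) = 16.0 + 8.05 = 24.05.

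**Step 3, power at 40 + 40, HR 0.44 (plan: 82%).**
- Schoenfeld: Φ(√(24.05/4) × |ln 0.44| − 1.96) = Φ(2.452 × 0.821 − 1.96) = Φ(0.053) = 0.521
- Freedman: Φ(√24.05 × (1 − 0.44)/(1 + 0.44) − 1.96) = Φ(4.904 × 0.389 − 1.96) = Φ(−0.053) = 0.479
- Simulated logrank test (exponential times, administrative censoring at 12 months): 0.502

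The methods differ by 4 points; the gap to 82% is about 30.

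**Step 4, what 82% would need.** Schoenfeld: 4 × (1.960 + 0.915)² / (ln 0.44)² = 49.1, so 50 events. Freedman: (1.960 + 0.915)² × (1.44/0.56)² = 54.7, so 55 events. At these event rates 82% takes 82 patients per group by Schoenfeld and 85 by simulation.

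**Step 5, power over the plan's expected 80 to 160 cases, even split.**

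| Cases | HR 0.44: Schoenfeld / Freedman / simulation | 15 points (HR 0.563): simulation |
|---|---|---|
| 80 | 0.521 / 0.479 / 0.502 | 0.304 |
| 120 | 0.693 / 0.646 / 0.674 | 0.424 |
| 160 | 0.812 / 0.770 / 0.796 | 0.535 |

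For 15 points at 80 cases the formulas agree with simulation: 0.310 (Schoenfeld), 0.296 (Freedman).

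**Step 6, what 40 + 40 can detect.** By simulation, power is 0.759 at HR 0.30, 0.794 at HR 0.28 and 0.803 at HR 0.275. So 80% is reached near HR 0.28, or 0.60 against about 0.87.

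**Step 7, the even split.** The plan's own assumptions point away from it: "Black patients will be much more likely to manifest ATTRm (Val122Ile) vs. ATTRwt CA", and 2.1.7 uses a "difference in the prevalence of ATTRm between Blacks and Hispanics (i.e., 0.08 vs 0.04, respectively"). Those rates give 600 × 0.08 + 200 × 0.04 = 56 ATTRm cases, leaving 24 ATTRwt at 80 cases. Simulated power for HR 0.44 is then 0.382. Schoenfeld gives about 0.50 there.

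**Step 8, alternative readings (Schoenfeld / Freedman).** One-sided 0.05: 0.644 / 0.603. The 0.60 read as progressed: 0.708 / 0.661. The 0.60 assigned to ATTRwt: 0.772 / 0.727. The 0.44 read as a risk ratio: 0.504 / 0.463. Values near 82% appear only with 80 per group (0.812 by Schoenfeld), follow-up of about 36 months (0.834 by Schoenfeld), or a one-sided test with 0.60 moved to ATTRwt (0.821 by Freedman). Each contradicts the text.

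**Secondary, medians.** With no dropout, a group of 40 reaches its median by 12 months only if at least 20 progress. The probability is 0.130 in ATTRm (binomial, 0.40) and 0.00002 in ATTRwt (binomial, 0.201).

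**The case against.** The arithmetic was not disputed. The objections concern weight, one assumption and the repair.

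- **Weight.** This is mainly a prevalence study. The synopsis places progression among the items to be explored, and the 800 is not derived from this calculation. The planned Kaplan-Meier and Cox estimates with intervals remain valid whatever the power. This is fair, but 2.1.1 lists the same comparison as a hypothesis to be tested, and a 30-point overstatement of power is material to it.
- **The time attached to 0.60.** The plan does not attach one. If 0.60 applied at 18 months, the 12-month difference would be 14.9 points, close to the printed 15. But power would still be about 52% even with 18 months of follow-up, and lower with 12. The 12-month reading is the natural one and should be declared as an assumption.
- **Source of the error.** A per-group 80 reported as the total would nearly explain the 82%. That is possible but not shown, and it would leave the 15 points wrong.
- **Limits of the recalculated figures.** The even split is an assumption. With 56 ATTRm and 104 ATTRwt at 160 cases, power is about 77% by simulation and 73% by Schoenfeld. Also, 160 of 800 is 20%, above the hypothesised prevalence of 10-15%, which gives 80 to 120 cases, the range Aim 2 uses. The 80% point depends on method: HR 0.30 by Schoenfeld, while Freedman gives 74% at HR 0.28. The walk component is observed only at visits, whereas the simulation uses continuous times. These points argue for stating method and assumptions; none brings power at 80 cases near 82%.
- **Medians.** An unreached median can simply be reported as such. That point is secondary, and the main conclusion does not need it.

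**Conclusion.** Both figures in 2.1.7 are wrong as written. At the stated inputs power is about 50%, some 30 points below the printed 82%, and HR 0.44 corresponds to 20 points, not 15. For the 15-point difference the plan names, power at 80 cases is about 30%, and at 160 evenly split cases still only about 54%. Power near 80% for HR 0.44 is reached only at 160 cases; within the 80 to 120 implied by the hypothesised prevalence it stays below 70%.

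These results rest on proportional hazards and on 0.60 being the 12-month value. The simulations also assume exponential times. An even split is assumed except where stated. No dropout is allowed for, although section 2.2 plans to censor patients who enter investigational trials; the resulting loss of events would lower power further.

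**What to change.** Check the source calculation to see which input was misreported, and make the two sentences in 2.1.7 agree. If the inputs stand as printed, replace them with wording such as:

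> With 80 cases (40 ATTRwt, 40 ATTRm) and 0.60 not progressed at 12 months in ATTRm, a two-sided logrank test at 0.05 has about 50% power for HR 0.44 (0.60 vs 0.80, a 20-point difference, about 24 events) and about 30% for a 15-point difference (0.60 vs 0.75, HR 0.56). Power of 80% is reached near HR 0.28 (0.60 vs about 0.87). For HR 0.44, power is about 67% with 120 cases and 80% with 160. Figures are from simulation with exponential times, an even split and no dropout.

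If 80 per group was intended, say so, reconcile it with the expected case numbers, and still correct the 15 points.

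As a secondary change in 2.1.8, summarise each group by the already planned Kaplan-Meier probability, taken at 12 months, and give the difference with a 95% CI beside the Cox HR. Report medians only if reached.

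The cost is new wording in 2.1.7 and one clause in 2.1.8. Enrolment and procedures do not change. The downside is a less favourable stated power for Hypothesis 4.

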AIM 2: Hypothesis 1 and 3: Means (95% CI) and/or medians (inter-quartile range) will be computed for all continuous measurements including RBP4/TTR concentrations. Pearson/Spearman correlation coefficients will be calculated to quantify the strength of the association between RBP4 plasma and urine concentrations in the overall ATTR CA cohort and separately by ATTRm vs. ATTRwt groups. Linear regression models will be used to assess differences in TTR kinetic stability between the two groups, adjusting for RBP4 concentration and vitamin A. **Hypothesis 2:** In addition to descriptive statistics, linear regression models will be employed to test the associations between RBP4 concentration, TTR stability, and cardiac amyloid scintigraphy heart to contralateral chest ratio between the two groups, ATTR CA vs non-amyloid HF controls, adjusting for clinical characteristics and retinol concentration.

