
serum vitamin A, and urinary creatinine, as a means to correct for confounding factors. *Unequal percentage of subjects with insulin resistance between groups*: As serum RBP4 concentration is increased in insulin resistance, to control for the potential confounder of unequal distribution of insulin resistance across our subject groups, we will adjust the analysis by history of diabetes and serum glucose. Our preliminary data has shown that glycated hemoglobin or lipids levels do not significantly interact with RBP4 concentrations in the target HFP EF population .

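### The >95% power for RBP4 rests on an unequal-variance comparison, but the Aim 2 analysis plan names only unqualified linear regression; with the default common variance, unadjusted power would be about 67–89%

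*Combined protocol and SAP*

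**What the plan says.** Section 2.1.7 sizes Aim 2 on 80–120 ATTR CA subjects against 680–720 non-amyloid subjects. It states: "These sample sizes generate >95% power to detect", under Hypothesis 1, "a minimum difference in RBP4 of 5, assuming SDs of 9 and 20 for ATTR CA and non-amyloid, respectively". The test behind the figure is not named. Earlier in the same section the expected split is wider: "we expect approximately 80-160 ATTR CA subjects and 640-720 non-amyloid controls".

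Section 2.1.8 sets all analyses "at a significance level of 0.05". For Aim 2 it plans the following:

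- **Hypotheses 1 and 3:** summaries of RBP4 and TTR concentrations (means with 95% CI, or medians), correlations between plasma and urine RBP4, and a linear regression whose outcome is TTR kinetic stability. RBP4 enters that regression as an adjustment variable.
- **Hypothesis 2:** "linear regression models will be employed to test the associations between RBP4 concentration, TTR stability" and the heart-to-contralateral ratio, in ATTR CA versus controls, adjusted for clinical characteristics and retinol. Which variable is the outcome is not said.

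Section 2.2, on insulin resistance as a confounder of RBP4, adds that "we will adjust the analysis by history of diabetes and serum glucose". That points to a covariate-adjusted model with RBP4 as outcome. None of these sections mentions a Welch test, robust standard errors or group-specific variances.

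**The concern.** The plan's own SDs imply variances of 81 and 400, a ratio of about five. The group with the larger variance is also six to nine times the larger group. A model with one residual variance takes that variance almost entirely from the controls and applies it to the small, less variable case group. The standard error of the difference is then too large, the test is too conservative, and the intervals are too wide.

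Linear regression, unqualified, is normally fitted with one residual variance. A software default could therefore give up much of the power the plan claims. Section 2.1.6 (Aim 2, Hypothesis 3) predicts lower plasma RBP4 in ATTR CA than in controls. That hypothesis has a power statement but no clearly specified test.

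**Working it through.** **Inputs.** Difference d = 5, SDs 9 (ATTR CA) and 20 (non-amyloid), group sizes 80 v 720 to 120 v 680: all from 2.1.7. Significance level 0.05: from 2.1.8. Two-sided testing is assumed; the documents state it only for Aim 1 ("A two-sided logrank test with an overall sample size of 80 subjects").

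**Step 1: the plan's figure.** With unequal variances, SE = √(9²/n₁ + 20²/n₂) and power = Φ(d/SE − 1.96).

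- 80 v 720: SE = √(1.0125 + 0.5556) = 1.252; power = Φ(3.993 − 1.96) = 97.9%.
- 120 v 680: SE = √(0.6750 + 0.5882) = 1.124; power = Φ(4.449 − 1.96) = 99.4%.

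The noncentral t gives 97.8% and 99.3%. Simulation (20,000 trials per setting) gives 97.8% and 99.4%. The stated >95% reproduces.

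**Step 2: the same data with a common variance.** This is the pooled t test, which equals unadjusted least squares with its default standard error. Pooled variance = [(n₁−1)·81 + (n₂−1)·400]/(n₁+n₂−2), and SE_pooled = SD_pooled·√(1/n₁ + 1/n₂). The test rejects beyond 1.96·SE_pooled, while the estimate still varies with the SE from Step 1. So power = Φ((d − 1.96·SE_pooled)/SE).

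- 80 v 720: variance = (79·81 + 719·400)/798 = 368.4, SD 19.19, SE_pooled 2.262; power = Φ((5 − 4.434)/1.252) = 67.4%.
- 120 v 680: variance = (119·81 + 679·400)/798 = 352.4, SD 18.77, SE_pooled 1.859; power = Φ((5 − 3.643)/1.124) = 88.6%.

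Simulation gives 67.2% and 88.4%.

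**Step 3: effect on error rate and intervals.**

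| Cases v controls | SE_pooled / SE | Actual type I error | Coverage of nominal 95% CI |
|---|---|---|---|
| 80 v 720 | 2.262/1.252 = 1.81 | 0.04% | 99.96% |
| 120 v 680 | 1.859/1.124 = 1.65 | 0.12% | 99.88% |

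**Step 4: sensitivity.**

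- *Covariates.* No R-squared is given. If covariates explained 10–40% of the variance in both groups (an assumed range) and left the 5-unit difference unchanged, common-variance power would be about 75–95% at 80 v 720 and 93–99% at 120 v 680. Reaching 95% would need about 41% and 17% respectively. Both SEs shrink by the same factor, so the ratios in Step 3 stay as they are.
- *More cases.* At 160 v 640, the top of the wider range in 2.1.7, common-variance power is 95.7%.
- *One-sided test.* Common-variance power would be 84.7% and 95.8%.

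**Step 5: the remedy.** In the unadjusted model, HC3 replaces s²/n by s²/(n−1) in each group. At 80 v 720 the SE is √(81/79 + 400/719) = 1.258 and power = Φ((5 − 1.96·1.258)/1.252), about 98%. At 120 v 680 the SE is √(81/119 + 400/679) = 1.127 and power is about 99%.

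**The case against.** The strongest reply is that the documents commit to no such error, and much of it stands.

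- **A reader might infer that the >95% is a miscalculation.** It is not. Giving two SDs implies an unequal-variance calculation, and that calculation reproduces the claim.
- **A reader might infer that the plan analyses RBP4 by ordinary least squares with one variance.** No section says so. The regression under Hypotheses 1 and 3 has TTR stability as its outcome, the Hypothesis 2 outcome is not identified, and section 2.2 promises adjustment without naming a model. A common variance is the usual default, not a stated choice.
- **A reader might infer that the study will miss its target difference one time in three.** That is the unadjusted figure at the lowest case count, and the planned models are adjusted. Sections 1.1.1 and 1.1.4.3 describe retinol as carried by RBP, so adjusting for retinol could change both the residual variance and the adjusted difference. Neither can be computed from the documents.
- **The error would be conservative.** It would not produce false positives, and it leaves the prevalence aim, enrolment and data collection untouched. The synopsis also lists RBP4 differences from controls among the exploratory items.

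What remains is that the plan assumes a five-fold variance ratio when it claims power, and then says nothing to stop an analyst from using a method that contradicts it. Adjustment may restore power, but if it helps both groups similarly it does not repair the intervals.

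**Conclusion.** The concern holds as a mismatch between the power basis in 2.1.7 and the analysis wording in 2.1.8. The stated >95% is right for a Welch or robust analysis (about 98–99%). Under a default common-variance fit without covariate gain it would be about 67% at 80 cases and 89% at 120, with intervals 1.81 to 1.65 times as wide as they need to be.

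These figures rest on the plan's SDs and difference, the Aim 2 group sizes, two-sided testing at 0.05 and no covariate adjustment. The loss is conditional on how the model is fitted, so this is a should-fix improvement rather than a fault that invalidates the design.

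**What to change.** - **Section 2.1.8, Aim 2:** name RBP4 as an outcome in ATTR CA versus non-amyloid controls. Fit the adjusted model with HC3 standard errors or with a separate residual variance per group. Use Welch's test for any unadjusted contrast.
- **Section 2.1.7:** state that the >95% power refers to that unequal-variance analysis, and that testing is two-sided if that is the intention. If a common-variance model is kept instead, restate the unadjusted power as about 67% (80 cases) to 89% (120 cases).

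The cost is a sentence or two of wording and a software option. No patients, visits, samples or data are affected.
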